## 11.2 Adverse events

### 11.2.1 Definitions and classification of adverse events

All AEs will be recorded in the CRF from informed consent until study completion or termination.

Adverse events will be coded according to MedDRA® version 19.0. Treatment-emergent adverse events (TEAEs) will be defined as events that have a start date on or after the first administration of study treatment in PS0018 until the last received dose of study medication +140 days (which covers the 20-week SFU Period). Adverse events occurring after this date will not be classified as TEAEs and will therefore be excluded from the summary tables. TEAEs will be categorized according to the PS0018 dose at onset, ie, the last dose being received at the time of onset of the event. If a TEAE occurs on the same day as a change in dosage and it cannot be clearly established whether or not the TEAE started before or after dosing, because for example the time of the AE is missing, then the TEAE will be attributed to the treatment dose that the subject has just completed, unless the adverse event is related to the injection (ie higher level term (HLT) of “injection site reactions”) or an anaphylactic reaction ([Section 14.3.7.1](#)), in which case the TEAE will be assigned to the treatment dose administered on that day. Tables will include columns for BKZ 160mg Q4W, BKZ 320mg Q4W, and All BKZ.

Any adverse events considered ongoing from PS0016 which do not worsen in severity during PS0018, or starting prior to first PS0018 dose will not be considered treatment emergent in PS0018 and will be tabulated separately.

In order to evaluate if there is any difference in the TEAE profile of subjects who have dose adjustments, additional summaries will be generated based on Dose adjustment described in [Section 3.6](#) for select tables as given in [Section 11.2.3](#).

Where dates are missing or partially missing, AEs will be assumed to be treatment-emergent, unless there is clear evidence to suggest that the AE started prior to PS0018 dosing. Handling of missing dates/times for classification of AEs as TEAEs is described in [Section 4.2.4](#).

All AEs will be coded and categorized by intensity (mild/moderate/severe) and relationship to study medication (related/not related).

In summaries including relationship to study medication, the following relationship categories will be included:

- Related
- Not related

Subjects who experience the same event multiple times will be included in the most related category for tabulations by maximum relationship. Events with missing relationship will be considered as 'Related' for summary purposes but shown as missing in the data listings.

In summaries including intensity, the following categories will be summarized:

- Mild
- Moderate
- Severe

Subjects who experience the same event multiple times will be included in the most severe category for tabulations by maximum intensity. Events with missing intensity will be considered as severe for summary purposes but shown as missing in the data listings.

All AE data will be presented as recorded in the database for the listings.

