### **4.2.4 Dates and times**

Partial dates may be imputed for the following reasons:

- Classification of AEs as treatment-emergent

- Classification of medications as prior or concomitant

Imputed dates will not be shown in the listings; all dates will be displayed as reported in the database.

The following rules will be applied for partial start dates with respect to the first dosing in PS0018:

- If only the month and year are specified and the month and year of first dosing is not the same as the month and year of the start date then use the 1st of the month. If time is missing this will be imputed as 00:00 h
- If only the month and year are specified and the month and year of first dosing is the same as the month and year of the start date, then use the date of first dosing. If this results in an imputed start date that is after the specified end date, then use the 1st of the month. If the imputed date is the date of first dosing then time will be imputed with the time of first dosing (ie event will be regarded as treatment-emergent)
- If only the year is specified, and the year of dosing is not the same as the year of the start date then use January 01 of the year of the start date. If time is missing this will be imputed as 00:00 h
- If only the year is specified, and the year of dosing is the same as the year of the start date, then use the date of first dosing in the given year. If this results in an imputed start date that is after the specified end date, then use January 01 of the year of start date. If the imputed date is the date of first dosing then time will be imputed with the time of first dosing (ie event will be regarded as treatment-emergent)
- If the start date is completely unknown, then use the date of first dosing. If this results in an imputed start date that is after the specified end date, then use January 01 of the year of the end date. If the imputed date is the date of first dosing then time will be imputed as the start time of first dosing (ie event will be regarded as treatment-emergent)

The following rules will be applied for partial stop dates:

- If only the month and year are specified, then use the last day of the month
- If only the year is specified, then use December 31 of the known year
- If the stop date is completely unknown, do not impute the stop date

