#### **14.3.7 Anaphylactic reaction**

Anaphylactic reactions will be summarized together in a stand-alone table with the following incidence rows:

- The first row within the body of the table will be labeled ‘Any hypersensitivity/anaphylactic reaction’ and will represent the overall incidence of subjects who reported at least one hypersensitivity reaction or at least one anaphylactic reaction.
- The second row within the body of the table will be labeled ‘Any hypersensitivity reaction’ and will represent the overall incidence of subjects who reported at least one hypersensitivity reaction.
- The third row within the body of the table will be labeled ‘Any anaphylactic reaction’ and will represent the overall incidence of subjects who reported at least one anaphylactic reaction.

Following these three overall incidence rows, all TEAEs that have been identified as either a hypersensitivity reaction or an anaphylactic reaction will be summarized by SOC, HLT and PT (these will not be presented by subcategory).

Hypersensitivity reactions and anaphylactic reactions will be identified as follows:

- **Hypersensitivity reactions:** all TEAEs with onset (start date/time) within 24 hours after any administration of study medication, which code to a PT which contains the term 'hypersensitivity' will be considered to be a hypersensitivity reaction and included in the summary table
- **Anaphylactic reactions:** An algorithmic approach will be used to identify TEAEs that are considered to be anaphylactic reactions. Preferred terms are separated into 4 distinct categories (A, B, C, D) prior to the algorithmic approach being applied.

All TEAEs with onset (start date/time) within 24 hours after any administration of study medication, and which fulfill any of the 3 criteria described in [Section 14.3.7.1](#) will be included in the summary table.

Any TEAEs with missing start time will be assumed to have occurred at the time of or after dosing for this purpose, if the event date is on the same day as a dosing date.

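### On a dose-change day, a hypersensitivity reaction of unknown timing is counted as following the new dose but tabulated under the old one

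*SAP*

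**What the plan says.** Two SAP sections govern such an event, and each makes its own presumption about timing.

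**Which events are counted (SAP 14.3.7).** The time window takes in "all TEAEs with onset (start date/time) within 24 hours after any administration of study medication". Inside that window, an event is a hypersensitivity reaction if its preferred term includes the word *hypersensitivity*. Where the clock time is absent and the event falls on a dosing date, "Any TEAEs with missing start time will be assumed to have occurred at the time of or after dosing for this purpose".

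**Which dose column they go in (SAP 11.2.1).** The rule is triggered when an event falls on a dose-change day and its order relative to the injection is unclear; a missing event time is given as an example. In that case, "then the TEAE will be attributed to the treatment dose that the subject has just completed". Two kinds of event are excepted. One is the injection-related event, identified by the HLT for injection site reactions. The other is set out in these words: "or an anaphylactic reaction ([Section 14.3.7.1](#)), in which case the TEAE will be assigned to the treatment dose administered on that day".

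Hypersensitivity reactions are defined in the body of 14.3.7. The cross-reference in 11.2.1 points only to the anaphylaxis algorithm in 14.3.7.1. Both kinds of reaction share one table of adverse events of special monitoring (AESM), with columns by PS0018 dose at onset (SAP 11.2.3, 14.3 and 14.3.7).

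**The concern.** An event with no start time on the day of a dose change is presumed to come after the injection when the SAP decides whether it belongs in the table, and before it when the SAP chooses the column. The authors evidently saw that acute reactions should go with that day's dose, because they wrote exceptions for two kinds of acute reaction. The third kind, which appears in the same table, was left out.

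The first secondary objective in both documents is the safety and tolerability of increasing from 160mg to 320mg. An acute reaction on the day of an increase bears directly on that objective. As written, it would appear against 160mg in the table set aside for such reactions.

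**Working it through.** The SAP gives no figure on this point to reproduce. The check has two parts: applying the rules, then a rate illustration.

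**1. Can the two rules be reconciled?** To be counted, the event must fall within 24 hours after some injection. On a dose-change day there are two candidates: that day's injection and the previous one. Protocol 7.2 sets Q4W doses 24 to 32 days apart, so the previous injection is far outside the window. Only that day's injection can qualify the event, so its place in the table already presumes that it followed the new dose. SAP 11.2.1 nevertheless sends it to the old dose.

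**2. Rules applied to an event of unknown order on a dose-change day**

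| Event | 160mg to 320mg day | 320mg to 160mg day |
|---|---|---|
| Preferred term containing *hypersensitivity*, outside the exceptions | 160mg | 320mg |
| *Type I hypersensitivity* (Category A in 14.3.7.1) | 320mg | 160mg |
| Other event flagged by the 14.3.7.1 algorithm | 320mg | 160mg |
| HLT injection site reactions | 320mg | 160mg |

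Only the first line goes against that day's dose.

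**3. Illustrative size.** From the SAP: up to 45 subjects (2.4), last dose at Week 44 (3.2.1.2), equations [13] and [15] for time at risk, and equation [19] for the exposure adjusted event rate (EAER). Assumed: S switchers, all increasing at Week 12 and staying on 320mg; everyone dosed through Week 44 and followed for the full 140 days; one reaction of unknown order on a first 320mg day.

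- Non-switcher, 160mg: 44 × 7 + 140 = 448 days.
- Switcher, 160mg by equation [13], Week 0 to Week 8 dose: 8 × 7 + 1 = 57 days.
- Switcher, 320mg by equation [15], Week 12 to Week 44 dose: 32 × 7 + 140 = 364 days.
- 160mg subject-years = [(45 − S) × 448 + S × 57] / 365.25.
- 320mg subject-years = S × 364 / 365.25.
- EAER = 100 × events / subject-years.

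For S = 5, the 160mg time is (40 × 448 + 5 × 57) / 365.25 = 18,205 / 365.25 = 49.84 years. The 320mg time is 1,820 / 365.25 = 4.98 years.

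| S (assumed) | Years 160mg / 320mg | EAER as written, 160mg / 320mg | EAER under the day's dose, 160mg / 320mg |
|---|---|---|---|
| 3 | 51.98 / 2.99 | 1.92 / 0 | 0 / 33.45 |
| 5 | 49.84 / 4.98 | 2.01 / 0 | 0 / 20.07 |
| 10 | 44.49 / 9.97 | 2.25 / 0 | 0 / 10.03 |
| 15 | 39.14 / 14.95 | 2.56 / 0 | 0 / 6.69 |

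In this example the event falls 12 × 7 = 84 days after the first dose, beyond the 57 days of 160mg risk time that the switcher contributes. That gap comes from equation [13] and is a separate matter. Crediting 84 days instead would change the S = 5 rate only from 2.01 to 100 / [(17,920 + 420) / 365.25] = 1.99.

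**The case against.** The strongest reply is that this is a slip in a cross-reference with almost no practical reach. SAP 14.3 groups hypersensitivity under the anaphylactic reaction heading, so the exception may have been meant to cover it. The rule applies only when the order cannot be clearly established. Protocol 7.2 has site staff give injections in clinic, injection times are recorded (SAP 11.1.1), and onset date/time is listed (SAP 11.2.3), so the order will often be known. The TEAE overview, TEAE incidence and serious TEAE tables are also produced by dose-adjustment group, where the event stays with the adjusters. Listings show days since the most recent dose.

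All of that stands, and it limits the size. It does not remove the contradiction: the text points to 14.3.7.1 alone, and programmers will follow the text. Nor does limiting the timing presumption to identifying reactions help, because the event is in the table only by virtue of that day's injection.

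A reader might infer more than the documents support:

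- **That every hypersensitivity reaction of unknown timing on an increase day goes to 160mg.** *Type I hypersensitivity*, other events flagged by 14.3.7.1 and events under the injection-site HLT already go to that day's dose.
- **That the error always favours 320mg.** It reverses on a return to 160mg. Multiple adjusters can also have more than one increase, so the number of affected days per subject is not fixed at one.
- **That the partial-date rules also push events to 160mg, since "If the start date is completely unknown, then use the date of first dosing".** SAP 4.2.4 limits imputation to classifying events as treatment-emergent and medications as prior or concomitant. It does not say that imputed dates decide the dose. Its rules also use the 1st of the month and January 01, which can fall after an increase. On dose attribution from partial dates the SAP is silent, and silence does not show a bias toward 160mg.

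**Conclusion.** The inconsistency is real and narrow. For a hypersensitivity reaction outside the two exceptions, on a dose-change day with order not established, SAP 14.3.7 and 11.2.1 make opposite presumptions, and the event lands in a column that contradicts the reason it was counted. Few such events are likely; the documents give neither a number of switchers nor an event rate. The All BKZ column and the dose-adjustment-group tables do not change.

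The effect is confined to the split between 160mg and 320mg. There, a single event can move the 320mg row of the hypersensitivity/anaphylaxis table between 0 and 1 subject. The rates above show the leverage of one hypothetical event under the stated assumptions and do not predict what the study will show. The point is worth correcting because it bears on the dose-increase objective and is easily put right.

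**What to change.** In SAP 11.2.1, widen the exception to cover injection site reactions (by HLT) and hypersensitivity or anaphylactic reactions as identified in Section 14.3.7, all assigned to the dose administered on that day. This replaces the present reference to 14.3.7.1 alone.

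The cost is one amended clause and a small change to the dose-at-onset derivation, which then carries through to the other dose-at-onset tables. No new data are needed and subject management is unaffected. The trade-off is that a reaction that in fact began before the injection would be assigned to the new dose, but 14.3.7 already makes that presumption when it counts the event. No rule assigning all ambiguous dates to 320mg is proposed.

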#### **3.2 Secondary objectives**

Secondary objectives of the study are:

- To assess the safety and tolerability of increasing the dose of bimekizumab from 160mg Q4W to 320mg Q4W for subjects with an inadequate response at Week 12
- To assess PK of bimekizumab
- To assess the immunogenicity of bimekizumab
- To assess the efficacy of open-label bimekizumab 160mg Q4W administered over 48 weeks

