#### **14.2.2 Other safety analyses**

Additional tables will summarize TEAEs by intensity and relationship to study medication, TEAEs leading to withdrawal from the study, treatment-emergent SAEs, and deaths.

In order to evaluate if there is any difference in the TEAE profile of subjects who have dose adjustments, additional summaries will be generated and are described further here. With respect to dose adjustments, subjects will be classified into 1 of the following 3 groups:

- Nonadjusters – This group consists of subjects who do not experience a dose adjustment during the study.
- Single adjusters – This group consists of subjects who experience just one dose adjustment during the study. Per the protocol, if just a single adjustment occurs, then that adjustment must be to go from bimekizumab 160mg Q4W to 320mg Q4W.
- Multiple adjusters – This group consists of subjects who experience more than 1 dose adjustment during the study. This means that the subjects in this group dose adjust from

---

bimekizumab 160mg Q4W to 320mg Q4W and then adjust back to 160mg Q4W (with further dose adjustments possible).

Summaries based on these 3 groups will be done by PS0016 randomized treatment group for the TEAE overview, incidence of TEAEs (by SOC, HLT, and PT), and incidence of treatment-emergent SAEs.

Extent of exposure to study medication in PS0018 will be summarized using descriptive statistics. As with the primary summaries of TEAEs, extent of exposure will be presented with columns for bimekizumab 160mg Q4W, bimekizumab 320mg Q4W, and All bimekizumab.

Change from Baseline in laboratory values, ECGs, and vital signs will be presented using descriptive statistics by PS0016 randomized treatment group and overall. As these variables are summarized over time and the initial values can be impacted by the randomized treatment in PS0016, the presentation by PS0016 randomized treatment group is intended to provide perspective on the change in these values starting with the initial PS0016 randomization through the 48-week Open-Label Treatment Period of PS0018. The table presentations will display descriptive statistics for the PS0016 Baseline and the observed and change from PS0016 Baseline results by scheduled visit for PS0018.

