#### 2.1.2 Secondary objectives

Secondary objectives of the study are:

- To assess the safety and tolerability of increasing the dose of bimekizumab from 160mg every four weeks (Q4W) to 320mg Q4W for subjects with an inadequate response at Week 12
- To assess pharmacokinetics (PK) of bimekizumab
- To assess the immunogenicity of bimekizumab
- To assess the efficacy of open label bimekizumab 160mg Q4W administered over 48 weeks

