### **3.6 Treatment assignment and treatment groups**

Treatment assignment for the SS and PK-PPS will be according to the actual treatment received in PS0018, unless stated otherwise in [Table 3–1](#). Analyses of efficacy data (based on the FAS) will be conducted according to the PS0016 randomized treatment group.

Subjects receiving the incorrect treatment (for example due to a dosing error) at a particular visit will be excluded from the PK-PPS as this would be considered as an important protocol deviation. Subjects may be excluded from the analysis at a particular visit (or visits) only, following discussion at the DEM.

Listings will be presented by subjects as randomized in PS0016. Summaries will be presented by treatment group and overall where applicable. See [Table 3–1](#) for the treatment assignment of the 3 different sets of treatment groups.

---

In the TFLs the treatment groups based on the PS0016 randomized treatment group will be displayed as follows, where BKZ refers to bimekizumab and PBO refers to placebo:

- BKZ 320mg + PBO
- BKZ 320mg
- All Subjects

In the TFLs the treatment groups based on the actual PS0018 treatment received (ie PS0018 dose at onset of event or measurement) will be displayed as follows:

- BKZ 160mg Q4W
- BKZ 320mg Q4W
- All BKZ

Lastly there will be the grouping based on dose adjustment in PS0018 defined as follows:

- Nonadjusters – This group consists of subjects who do not experience a dose adjustment during the study.
- Single adjusters – This group consists of subjects who experience just one dose adjustment during the study. Per the protocol, if just a single adjustment occurs, then that adjustment must go from bimekizumab 160mg Q4W to 320mg Q4W.
- Multiple adjusters – This group consists of subjects who experience more than 1 dose adjustment during the study. This means that the subjects in this group dose adjust from bimekizumab 160mg Q4W to 320mg Q4W and then adjust back to 160mg Q4W (with further dose adjustments possible).

For summary purposes, the single and multiple adjuster groupings will be combined.

The treatment group labels and tabulation requirements for each data type are displayed in [Table 3–1](#) **Error! Reference source not found.**

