### 11.2.3 Presentation of adverse events

An overview of the number and percentage of subjects who experience TEAEs will be presented based on the SS. This tabulation will include the number and percentage of subjects with any TEAEs, serious TEAEs, related TEAEs, discontinuation due to TEAEs, severe TEAEs, AEs leading to death and TEAEs leading to death; event counts will also be included.

- The tabulation will be presented by PS0018 dose at onset.
- This tabulation will be repeated by Dose adjustment and PS0016 randomized treatment group.

In addition, the following summaries will be presented by PS0018 dose at onset, SOC, high level term (HLT) and PT, based on the SS:

- Incidence of TEAEs by PS0018 dose at onset, including the EAIR and EAER calculated as described in [Section 11.2.2](#) for the 'Any TEAE' category only
- Incidence of TEAEs by PS0018 dose at onset, including the EAIR and EAER calculated as described in [Section 11.2.2](#) for the 'Any TEAE' category only by overall ADA status (positive/negative)
- Incidence of TEAEs by Dose adjustment and PS0016 randomized treatment group
- Incidence of serious TEAEs by PS0018 dose at onset and Dose adjustment
- Incidence of TEAEs by relationship and PS0018 dose at onset
- Incidence of TEAEs by maximum relationship and PS0018 dose at onset
- Incidence of TEAEs by maximum intensity and PS0018 dose at onset
- Incidence of fatal TEAEs by relationship and PS0018 dose at onset

- Incidence of serious TEAEs by relationship and PS0018 dose at onset
- Incidence of non-serious TEAEs above threshold of 5% of subjects by PS0018 dose at onset
- Incidence of non-serious TEAEs above threshold of 5% of subjects by relationship and PS0018 dose at onset
- Incidence of ongoing AEs from PS0016
- Incidence of ongoing AEs from PS0016 which do not worsen in severity, or AEs started prior to PS0018 dose, by PS0016 randomized treatment group

In addition, separate AE summaries by PS0018 dose at onset, SOC, HLT and PT will be included for the following AEs of special monitoring (AESM) further defined in [Section 14.3](#).

- Major cardiovascular events
- Serious infections, including opportunistic infections and tuberculosis (TB)
- Malignancies including lymphoma
- Cytopenias
- Neuropsychiatric events (in particular, depression and suicide)
- Inflammatory bowel disease
- Anaphylactic reaction (hypersensitivity and anaphylactic reactions)
- Hepatic events and drug-induced liver injury

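### The TEAE tables by dose adjustment mix events from before the increase with unequal follow-up and carry no exposure adjustment, so a column difference need not reflect the dose increase

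*SAP*

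**What the plan says.** A secondary objective concerns the "safety and tolerability of increasing the dose of bimekizumab from 160mg every four weeks (Q4W) to 320mg Q4W" (SAP 2.1.2; Protocol 3.2 has the same objective).

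Two sets of TEAE tables bear on it. The first is by PS0018 dose at onset, with 160mg, 320mg and all-bimekizumab columns, and EAIR and EAER for the Any-TEAE row (SAP 11.2.3). The second is by dose adjustment. Its stated purpose is to "evaluate if there is any difference in the TEAE profile of subjects who have dose adjustments" (SAP 11.2.1). It includes a repeat of the TEAE overview and "Incidence of TEAEs by Dose adjustment and PS0016 randomized treatment group" (SAP 11.2.3). It follows Protocol 14.2.2: "Summaries based on these 3 groups will be done by PS0016 randomized treatment group for the TEAE overview", together with TEAE incidence and serious TEAEs.

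Group membership is decided over the whole study. For nonadjusters: "This group consists of subjects who do not experience a dose adjustment during the study". For single adjusters: "This group consists of subjects who experience just one dose adjustment during the study" (SAP 3.6). Single and multiple adjusters are pooled for summaries (SAP 3.6, 3.9). An increase is possible only from Week 12 (SAP 2.3).

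The TEAE window is the same for everyone: "events that have a start date on or after the first administration of study treatment in PS0018 until the last received dose", plus 140 days (SAP 11.2.1). It does not restart at the increase. The dose-adjustment tables are to show numbers and percentages of subjects and event counts. EAIR and EAER are specified only for the dose-at-onset TEAE tables and the tables of adverse events of special monitoring (SAP 11.2.3, 14.3).

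**The concern.** Subjects are sorted by something that happens after baseline, while their events are counted from baseline. This has two consequences.

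- An adjuster's events during 12 or more weeks on 160mg sit in the adjuster column. So do a multiple adjuster's events after returning to 160mg.
- An adjuster has to be on treatment at Week 12 or later to become one. Nonadjusters have no such condition, so they include everyone who left before Week 12 and everyone withdrawn at Week 12 for not reaching PASI50. SAP 4.2 expects missing data from treatment discontinuation to be common.

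Without an exposure-adjusted rate, the reader cannot separate these effects from the dose increase. A follow-up difference could pass for a dose effect, or a real change after the increase could be diluted. The study's primary safety variable is exposure-adjusted, but these tables are not, although follow-up can differ between their columns by construction. For PASI, SAP 8.2.1 already re-baselines adjusters at the visit where 320mg starts. Safety has no counterpart.

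**Working it through.** **Inputs from the documents.** Last scheduled dose at Week 44 (SAP 3.2.1.2); time at risk = last dose − first dose + 140 days (SAP 11.1.2); earliest increase at Week 12 (SAP 2.3). The documents give no event rate, dropout rate or expected number of adjusters, so those used below are assumptions.

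**The plan's own figure.** 44 × 7 + 140 = 308 + 140 = 448 days = 64 weeks, which matches the stated maximum duration.

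**Share of a completing adjuster's window before the increase** = 7w / 448 for an increase at Week w:
- Week 12: 84/448 = 18.8%
- Week 24: 168/448 = 37.5%
- Week 32: 224/448 = 50.0%
- Week 44: 308/448 = 68.8%

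**Shortest windows**, absent death or loss to follow-up:
- Nonadjuster with one dose: 140 days
- Nonadjuster stopped at Week 12, last dose Week 8: 56 + 140 = 196 days
- Adjuster with one 320mg dose at Week 12: 84 + 140 = 224 days

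**Group comparison with no dose effect.** With a constant first-event rate r per year, P(t) = 1 − exp(−r × t/365.25). All adjusters are assumed to complete (448 days). A fraction d of nonadjusters is assumed to leave early with 140 or 196 days, giving d × P(early) + (1 − d) × P(448).

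| Rate per 100 subject-years | Adjusters | Nonadjusters, d = 20% | Nonadjusters, d = 40% | Excess in adjusters (points) |
|---|---|---|---|---|
| 50 | 45.8% | 40.2–41.4% | 34.5–36.9% | 4.4–11.3 |
| 100 | 70.7% | 62.9–64.8% | 55.1–59.0% | 5.9–15.6 |
| 200 | 91.4% | 83.8–86.3% | 76.3–81.2% | 5.1–15.1 |

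**Events before the increase.** At 100 per 100 subject-years, the share of affected adjusters whose first TEAE precedes the increase is P(84)/P(448) = 29.1% for an increase at Week 12, and P(168)/P(448) = 52.2% for Week 24.

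**Dilution of a real effect.** Suppose the rate doubles after a Week 12 increase, with base rate 100 per 100 subject-years and equal follow-up. Adjusters: 1 − exp(−(84 + 2 × 364)/365.25) = 89.2%. Nonadjusters: 70.7%. The ratio of percentages is 1.26.

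**The sign can reverse.** At 100 per 100 subject-years, an adjuster with only the guaranteed 224 days has P(224) = 1 − exp(−0.613) = 45.8%, against 70.7% for a nonadjuster who completes.

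**Precision after a split.** Assume 9 adjusters, all increased at Week 12 and completing: 9 × 364/365.25 = 8.97 subject-years after the increase. By SAP equation 18, zero events gives a rate of 0 (95% CI 0 to 41.1) per 100 subject-years. Three subjects with an event give 33.4 (6.9 to 97.7). The upper limit with zero events is 74.0 for 5 adjusters and 26.4 for 14.

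**The case against.** The strongest reply is that the dose-adjustment tables are supplementary. Dose is addressed mainly by the dose-at-onset tables, which assign each event to 160mg or 320mg and give Any-TEAE rates, alongside rates for adverse events of special monitoring and exposure by dose. The objective does not itself ask for a before/after contrast. The overview includes event counts as well as percentages. Serious TEAEs are planned by dose at onset and dose adjustment and, if crossed, would already separate events on each dose. Listings flag 320mg timepoints (SAP 3.1) and give dose at onset (SAP 11.2.3), so with up to 45 subjects each sequence can be read directly.

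Much of this stands. A reader might infer that the dose-increase objective has no usable analysis; the documents do not support that. A reader might also infer that adjusters must look worse. That fails too: adjusters are selected at a PASI response just above the withdrawal threshold and may themselves leave early.

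What remains is that the dose-at-onset 160mg column pools all subjects, so it does not show adjusters before their increase. SAP 11.2.2 also starts the clock for subjects with an event at the first PS0018 dose, so a 320mg denominator can include 160mg time. The wording of the serious-TEAE table does not say whether it is crossed, and that table covers serious events only.

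**Conclusion.** The point holds for the TEAE overview and TEAE incidence tables by dose adjustment. As specified, they cannot separate the dose increase from follow-up length or from events that preceded it. For a completing adjuster, 19% to 69% of the at-risk window precedes the increase. The spurious excess is roughly 4 to 16 points under the working's assumptions of no dose effect, all adjusters completing, 20 to 40% early dropout among nonadjusters and 50 to 200 events per 100 subject-years. Actual dropout decides both size and direction.

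A larger gap might be inferred by setting a completing adjuster (448 days) against a Week 12 withdrawal (196 days): at 150 per 100 subject-years, 84% against 55%. That contrasts two extreme individuals; the tables compare groups. The dose-at-onset tables cover the objective in part, so this is an inexpensive improvement to supportive displays and leaves the primary safety analysis as planned.

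**What to change.** In SAP 11.2.3:

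1. Keep the adjuster and nonadjuster columns, which follow the protocol's grouping, and add subject-years and Any-TEAE EAIR and EAER to them.
2. Add a supportive table for adjusters that splits TEAEs and time at risk at the first 320mg dose. Show separately, or flag, events after any return to 160mg. Start the clock for the later period at the first 320mg dose.
3. Alongside it, show nonadjusters still on treatment at Week 12, with events and time counted from Week 12.
4. State that serious TEAEs by dose at onset and dose adjustment are crossed.
5. Footnote that the contrast is descriptive and confounded with calendar time, and that the pre-increase rate is biased low because adjusters had to remain on treatment to be increased.

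The cost is SAP wording and re-cut tables. No new data are needed: dose dates are recorded and time at risk is already derived per dose interval (SAP 11.1.1, 11.1.2). SAP 1 gives the route: an amendment before database lock, or an additional analysis explained in the CSR afterwards. Cells will be small. The Week 12 landmark also matches later increases only approximately.
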